Week 8: Participant to return to The Hospital for Sick Children. Study treatment increased as tolerated by 2mg/kg/day CBD, neurological and physical examination will be performed, weight recorded, seizure diary evaluated. Medical history including concomitant medications will be reviewed. If at maximally tolerated study treatment dose as determined by study team, then bloodwork will be performed (CBC, LFT, and Renal profile and trough AED levels) and QOLCE completed by caregiver/parent. The Pediatric Epilepsy Side Effect Questionnaire (PESQ) will be completed by parent/legal guardian to assess for any adverse events and tolerability.

Week 12: Participant to return to The Hospital for Sick Children for clinical evaluation, which includes an interview to assess current clinical condition, any participant, parent/

legal guardian concerns related to TIL-TC150 and assess for any adverse effects and tolerability by interview. A neurological and physical examination will be performed, weight recorded, seizure diary evaluated. Medical history including concomitant medications will be reviewed. Participant should be on maximal dose of 8mg/kg/day or max tolerated dose now, or on maximally tolerated dose (as determined by study team). If at maximally tolerated study treatment dose as determined by study team, then bloodwork will be performed (CBC, LFT, and Renal profile and trough AED levels). The Pediatric Epilepsy Side Effect Questionnaire (PESQ) will be completed by participant parent / legal guardian to assess for any adverse events and tolerability.

Week 16: Participant to return to The Hospital for Sick Children for clinical evaluation, neurological and physical examination will be performed, weight recorded, and seizure diary will be evaluated. Medical history including concomitant medications will be reviewed. If target dose only reached at this stage blood work to be done now, if previously performed at target or maximally tolerated doses no need to repeat. The Pediatric Epilepsy Side Effect Questionnaire (PESQ) will be completed by participant parent/legal guardian to assess for any adverse events and tolerability and QOLCE completed by caregiver/parent between weeks 16 – 20. In addition, the family will be contacted by clinical psychology to complete a follow-up Vineland adaptive behaviour assessment to measure any changes in behaviour.

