### 5.7 Longitudinal safety and tolerability phase (44 weeks)

This is a continuation of the study beyond the initial 20-week intervention to continue to assess participants who chose to continue with TIL-TC150 therapy beyond the primary analysis period.

Week 28: Participant to return for clinical evaluation (including physical and neurological examination) as they have decided to continue TIL-TC150. Their dose will be 16mg/kg/day CBD divided twice daily or their individual maximally tolerated dose during

the intervention period. Their seizure diary will be reviewed. The Pediatric Epilepsy Side Effect Questionnaire (PESQ) will be completed to assess for any adverse events and tolerability and QOLCE completed by caregiver/parent.

Week 40: Participant to return for clinical evaluation (including physical and neurological examination) and seizure diary reviewed. The Pediatric Epilepsy Side Effect Questionnaire (PESQ) will be completed by participant parent/legal guardian to assess for any adverse events and tolerability. Bloodwork will be performed once to check CBC, LFT, and Renal profile and trough AED levels during weeks 40-64.

Week 52: Participant to return for clinical evaluation (including physical and neurological examination) and seizure diary reviewed. The Pediatric Epilepsy Side Effect Questionnaire (PESQ) will be completed by participant parent/ legal guardian to assess for any adverse events and tolerability and QOLCE completed by caregiver/parent. Bloodwork will be performed to check CBC, LFT, and Renal profile and trough AED levels. If the blood work is done at week 40, then no need to repeat.

Week 64: Participant to return for clinical evaluation (including physical and neurological examination) and seizure diary reviewed. The Pediatric Epilepsy Side Effect Questionnaire (PESQ) will be completed to assess for any adverse events and tolerability by caregiver/parent. For families who choose to continue therapy for the longer term, they will be invited to complete a Vineland assessment during 52-64 weeks by the psychology team in our study to measure any changes in behaviour. Bloodwork will be performed to check CBC, LFT, and Renal profile and trough AED levels. If the blood work is done at week 40 or 52, then no need to repeat.

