|                                 | 1             | Telephone and/ or email contact by study team to determine dosing and tolerability   | Once tolerance ensured, increase dose to 4mg/kg/day CBD divided twice daily  |

|    |  |   |
|----|--|---|
| 2  | Clinic visit – tolerance review, adverse events,; physical and neurological exam; parent/legal guardian to complete PESQ; seizure diary review   | Once tolerance ensured, increase to 6mg/kg/day CBD divided twice daily  |
| 3  | Telephone and/ or email contact by study team to determine dosing and tolerability   | Once tolerance ensured, increase to 8mg/kg/day CBD divided twice daily  |
| 4  | Clinic visit – tolerance review, adverse events; physical and neurological exam; parent/legal guardian to complete PESQ; seizure diary review; bloodwork   | Once tolerance ensured, increase to 10mg/kg/day CBD divided twice daily |
| 5  | Telephone and/ or email contact by study team to determine dosing and tolerability   | Once tolerance ensured, increase to 12mg/kg/day CBD divided twice daily |
| 6  | Telephone and/ or email contact by study team to determine dosing and tolerability   | Once tolerance ensured, increase to 14mg/kg/day CBD divided twice daily |
| 7  | Telephone and/ or email contact by study team to determine dosing and tolerability   | Once tolerance ensured, increase to 16mg/kg/day CBD divided twice daily |
| 8  | Clinic visit – tolerance review, adverse events; physical and neurological exam; parent/legal guardian to complete PESQ and QOLCE; seizure diary review; bloodwork performed once child is at target / maximal tolerated dose (any stage from week 8-16) | If tolerated, dose to continue at 16mg/kg/day CBD divided twice daily   |
| 10 | Telephone and/ or email contact by study team to determine dosing and tolerability   | If tolerated, dose to continue at 16mg/kg/day CBD divided twice daily   |
| 12 | Clinic visit – tolerance review, adverse events; physical and neurological exam; parent/legal guardian to complete PESQ; seizure diary review; bloodwork performed once at target / maximal tolerated dose (if not done previously)                      | If tolerated, dose to continue at 16mg/kg/day CBD divided twice daily   |
| 14 | Telephone and/ or email contact by study team to determine dosing and tolerability   | If tolerated, dose to continue at 16mg/kg/day CBD divided twice daily   |

|                                      |       |  |   |
|--------------------------------------|-------|--|---|

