## 7.2 Methods of assessing

During the intervention period and follow-up there will be regular clinic review and telephone/email evaluation of the participant to assess tolerability of the study treatment and screen for any adverse events. This will be done by direct questioning of participant, parent/caregiver at each review. In addition the study team will perform a physical and neurological examination of participant at each clinic review. Every clinic visit we will ask parent/ caregiver to complete a side effect questionnaire (PESQ questionnaire) and study team will review the daily seizure diary. In addition at regular

intervals during the study the participant will have bloodwork to evaluate hematopoiesis, liver and renal function and trough AED levels.

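### Dosing and blood-work instructions conflict at the top dose: by default the last scheduled panel before the Week 20 safety report falls about 1 week (table) or 5 weeks (5.6 text) into 16 mg/kg/day

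*Combined protocol and SAP*

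**What the plan says.** **Role of blood work.** Section 2 names renal, hematologic and hepatic blood work and AED levels among the measures of dosing safety. Section 7.2 plans, at regular "intervals during the study the participant will have bloodwork to evaluate hematopoiesis, liver and renal function and trough AED levels". The primary endpoint is the maximal safely tolerated dose (3.4), reported at the end of the Week 16-20 period (3.2).

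**Dose.** Section 5.2 starts at 2 mg/kg/day and adds 2 every 7 days up to 16. The Week 7 row of the Schedule of Events table (5.8) reads "Once tolerance ensured, increase to 16mg/kg/day CBD divided twice daily", and from Week 8 the table only continues that dose. Section 3.2, however, names Week 8 for the last increase, and the Week 8 paragraph of 5.6 includes another step of 2 mg/kg/day as tolerated. The Week 12 paragraph of 5.6 says "Participant should be on maximal dose of 8mg/kg/day or max tolerated dose now".

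**Panels at maximum dose.**
- 5.6 text, Weeks 8 and 12, in the same words: "If at maximally tolerated study treatment dose as determined by study team, then bloodwork will be performed". Week 12 carries no waiver.
- Table, Week 8: "bloodwork performed once child is at target / maximal tolerated dose (any stage from week 8-16").
- Table, Weeks 12 and 16: "bloodwork performed once at target / maximal tolerated dose (if not done previously").
- 5.6 text, Week 16: "if previously performed at target or maximally tolerated doses no need to repeat".

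Neither version lists blood work after the Week 16 visit up to Week 20. The next panel is taken once in Weeks 40-64, in children who continue (5.7 and table).

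**The concern.** Two dosing statements in operative text are wrong as they stand. The Week 12 maximum is half the protocol maximum, and a Week 8 step for a child already at 16 mg/kg/day would break the cap.

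The panel instructions then differ for exactly the children who titrate on schedule. Followed literally, the text gives them a second panel at maximum dose at Week 12 and the table does not. The laboratory part of the Week 20 safety statement would rest on different lengths of exposure depending on which section staff follow, and nothing requires the report to show this.

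AED levels matter too. Section 1.7.1 says that CBD may raise the levels of other drugs, and section 1.5 allows AED doses to be adjusted on the level found. After an adjustment at Week 8, the next scheduled level is at Week 12 on the text, but in Weeks 40-64 on the table.

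**Working it through.** **Inputs.** Start 2 mg/kg/day, step 2 every 7 days, cap 16 (5.2). Week 0 is the first dose (5.2, 5.6). Visit window ±3 days (5.7). Safety report at Week 20 (3.2).

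**Dose path.** Dose at Week k = min(2 + 2k, 16). This gives 4, 6, 8, 10, 12, 14, 16 at Weeks 1 to 7, which reproduces every row of the table. One more step at Week 8 would give 2 + 2×8 = 18, which is 2 above the cap. The 8 mg/kg/day named at Week 12 is the Week 3 dose on this path.

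**Time at 16 mg/kg/day at the last panel.** Week 7 is day 49 and Week 20 is day 140, so an on-schedule child has 140 − 49 = 91 days at 16 mg/kg/day. Ranges move the panel by ±3 days.

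| Version followed | Last panel | Days at dose | Days from panel to Week 20 | Share of the 91 days |
|---|---|---|---|---|
| Table, default | Week 8, day 56 | 56 − 49 = 7 (4-10) | 140 − 56 = 84 (81-87) | 92% (89-96%) |
| 5.6 text | Week 12, day 84 | 84 − 49 = 35 (32-38) | 140 − 84 = 56 (53-59) | 62% (58-65%) |

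**Two qualifications.**
- The table's window is Weeks 8-16, so its single panel may be drawn later. At Week 16 it would fall 16 − 7 = 9 weeks into the dose. One week is therefore the default and the minimum on this dose path, not a fixed value.
- If the child reaches 16 mg/kg/day only at the Week 8 visit, the default figures become 8 − 8 = 0 weeks (table) and 12 − 8 = 4 weeks (text).

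**Who is affected.** The two versions part only for a child already drawn at maximum dose at Week 8. A child who reaches maximum between the Week 8 and Week 12 visits is drawn at Week 12 on the text and by default on the table, and is then waived at Week 16 on both.

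**Number of panels by Week 20, on-schedule child.** Table: Weeks 0, 4, 8 = 3. Text: Weeks 0, 4, 8, 12 = 4.

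**Next scheduled panel, continuers only.** Table: 40 − 8 = 32 to 64 − 8 = 56 weeks later. Text: 40 − 12 = 28 to 64 − 12 = 52 weeks later.

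**The case against.** **The text can be read as one panel.** The Week 12 sentence repeats the Week 8 sentence and says nothing about earlier draws. Section 1.5 plans AED levels at baseline and at the maximal tolerated dose, section 5.3 (Concomitant treatments) defers level timing to the detailed schedule, and the Week 16 waiver could be read back onto Week 12. This stands as a possible reading. Against it, the narrative writes waivers out where it wants them: at Week 16, at Week 52 ("If the blood work is done at week 40, then no need to repeat") and at Week 64. An instruction that can be read both ways still needs settling.

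**Week 8 in 3.2 may mean the eighth treatment week.** Counting the first week as 1, that agrees with the table. It does not rescue the Week 8 paragraph of 5.6, which uses the table's numbering and still includes a step.

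**The 8 mg/kg/day is an isolated slip.** It is. A reader might infer from it that the Week 12 paragraph is outdated and that staff cannot tell which blood-work rule is current. The documents do not support that: a wrong dose figure says nothing about which panel rule governs.

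**Other monitoring continues.** Examinations and PESQ at Weeks 12 and 16, contacts at Weeks 10, 14 and 18, immediate evaluation of suspected events (7.1), and the investigators' review after every third patient (1.5) all remain. The draw for suspected toxicity noted under the table names only an AED trough, but nothing bars a fuller panel on suspicion. This limits the point to changes without symptoms.

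**The Week 16 waiver is deliberate.** A reader might infer that omitting a Week 16 panel is itself an error. Text and table agree on that waiver, and the documents give no time course for laboratory change, so the value of the extra draw cannot be quantified.

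**Conclusion.** The point holds as an internal contradiction with a limited consequence. The 8 mg/kg/day maximum at Week 12 and the Week 8 step for a child already at 16 are wrong as written. The Week 12 panel is ordered in one place and waived in the other. By default, the last scheduled panel before the safety report comes about 1 week (table) or 5 weeks (text) after an on-schedule child reaches 16 mg/kg/day; a last step at the Week 8 visit makes these 0 and 4 weeks.

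These figures assume no held or delayed steps beyond those stated, and under the table a panel at the first opportunity. Children who stop escalating early have longer at their own maximum at each panel. The percentages are calendar shares, not detection rates. Only silent liver, renal, blood-count or AED-level change is at issue. The documents do not support a claim that children go unmonitored, or that a compulsory Week 16 panel is needed to correct an error.

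**What to change.** 1. **Week 12 dose (5.6).** Change 8 to 16 mg/kg/day.
2. **Last increase.** In 3.2, state Week 7, on the table's numbering, as the last on-schedule increase. In the Week 8 paragraph of 5.6, limit the step to children still below 16 mg/kg/day.
3. **Week 12 panel.** In the Week 12 row of the table, delete the condition that waives the panel if one was done before, so that every child at target or maximally tolerated dose has the panel the 5.6 text already orders.
4. **Reporting.** Give days at current dose with each panel, and limit the Week 20 laboratory safety statement to those durations.

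**Cost.** A short amendment. Item 3 adds no draw beyond the 5.6 text. Against the table it adds one venepuncture for each child already drawn at Week 8 (3 panels to 4; at most 20 × 1 = 20 draws), at an existing visit. That is a real burden in young, developmentally impaired children. Items 1, 2 and 4 add no procedure.

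**Optional.** A Week 16 panel for all children still on treatment would fall 112 − 49 = 63 days (60-66) into 16 mg/kg/day for an on-schedule child and leave 28 days (25-31) to Week 20, for one further draw. The sponsor may reasonably decline it if item 4 is adopted.

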## **2. Study Objectives**

The primary objective is to establish the safe dosing and tolerability of TIL-TC150, a CBD rich cannabis plant extract administered as an oral solution for children with severe refractory epilepsy. Dosing safety will be measured by blood work evaluation of renal, hematologic and hepatic function and of AED levels, by parent/caregiver report, by physician assessment, and by assessing caregiver reported tolerability and the Pediatric Epilepsy Side Effects Questionnaire (PESQ).

As secondary measures we will also assess:

1. The impact of therapy on quality of life using the Quality of Life in Childhood Epilepsy (QOLCE) questionnaire and on everyday behaviours using the Vineland Adaptive Behavior Scales, Second Edition.

2. Change in seizure frequency from baseline using the following measures:

Parent-reported seizure diary

24 hour Ambulatory EEG study (measurements: (a) percentage change in electrographic seizure frequency and (b) using spike detection software we will measure the percentage change in interictal activity during the recording)

Number of episodes of Status Epilepticus – defined as convulsive seizure lasting longer than 10 minutes

Frequency of use of rescue medications (Lorazepam, Midazolam, or Diazepam).

Number of visits to emergency department / hospitalizations with seizures

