### 3.2 Intervention period (20 weeks)

Following the pre-intervention assessment of baseline seizure frequency, the participant will commence TIL-TC150 product. The initial dose is 2mg/kg/day CBD divided twice daily with weekly titration as described below in section 5. Study treatment will be increased each week as tolerated by 2mg/kg/day CBD. Week 8 should be the last increase if the participant increases by this schedule. The maximal dose is 16/mg/kg/day CBD.

During this time there will be regular communication and clinic visits with the investigator team, as detailed in section 5. Once 16 weeks of therapy have been completed, participants will enter a 4 week interim analysis period, during which time they continue the TIL-TC150 at an unchanged dose and a 4 week seizure diary and a 24 hour ambulatory EEG recording will be performed and compared with the pre-intervention seizure frequency.

This primary outcome data regarding safety, tolerability, dosing and secondary seizure outcomes will be reported at this time point.

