### 5.2 Treatment Regimen

Each participant will start the treatment with a dose of 2mg/kg/day CBD given in two equal doses each day. The first dose will be given during the Baseline (Week 0) visit. Following this dose the participant will be observed by study personnel for a period of 2 hours. The participant's parent/legal guardian will increase the participant's dose by 2mg/kg/day CBD every 7 days as tolerated, to a maximal dose of 16mg/kg/day CBD. Once optimal dose is determined for each participant they may continue the treatment for the duration of study follow-up and thereafter it will be continued if wished by participants.

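### The Week 12 text of section 5.6 gives the maximal dose as 8 instead of 16 mg/kg/day; a minor, optional point is that no PESQ is scheduled between the Week 16 visit and the Week 20 report

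*Combined protocol and SAP*

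**What the plan says.** **Maximal dose.** The Week 12 paragraph of section 5.6 reads "Participant should be on maximal dose of 8mg/kg/day or max tolerated dose now". Section 5.2 has the parent raise the dose by 2 mg/kg/day every 7 days "to a maximal dose of 16mg/kg/day CBD". The Week 12 row of the 5.8 table says "If tolerated, dose to continue at 16mg/kg/day CBD divided twice daily". The Study Summary and sections 1.5, 3.2 and 5.7 also give 16 mg/kg/day. Section 3.4 makes the highest safely tolerated dose the primary endpoint.

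**Bloodwork.** The Week 12 paragraph calls for blood tests if the study team judges the child to be at the maximally tolerated dose. The Week 16 paragraph says that tests already done at the target or maximally tolerated dose need not be repeated. The next scheduled draw is a single one in Weeks 40 to 64, for children who continue.

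**PESQ.** Section 2 lists the Pediatric Epilepsy Side Effects Questionnaire among several measures for the primary objective. Section 7.2 attaches it to clinic visits: "Every clinic visit we will ask parent/ caregiver to complete a side effect questionnaire (PESQ questionnaire"). Sections 5.6 to 5.8 place it at Weeks 2, 4, 8, 12 and 16, then at Week 28 for children who continue. The Week 16 sentence runs "to assess for any adverse events and tolerability and QOLCE completed by caregiver/parent between weeks 16" to 20. The 16–20 row of 5.8 lists a Week 18 phone or email contact, the Vineland, the diary and the EEG, but no PESQ. Section 3.2 says of the end of that window: "This primary outcome data regarding safety, tolerability, dosing and secondary seizure outcomes will be reported at this time point".

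**The concern.** The trial exists to find how much of the product these children tolerate, and one of its visit instructions names a ceiling at half the intended one. Staff working from the Week 12 paragraph could accept 8 mg/kg/day as the end of titration for a child who might have gone further. They could also take the on-target safety bloods at that dose and regard the requirement as met. If the child later went up to 16, no further full safety panel would be scheduled until Week 40 at the earliest. The table note on suspected toxicity allows an extra draw for AED levels only.

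The lesser matter is timing. The PESQ is the only side-effect questionnaire named in section 2. The primary evaluation window has its own diary and EEG, and the QOLCE and Vineland can be completed in it, but it has no later PESQ. For a child who titrates slowly, the last PESQ before the primary report may come soon after the final increase.

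**Working it through.** **Step 1: reproduce the maximum.** Inputs: start at 2 mg/kg/day, add 2 every 7 days, stop at 16 (section 5.2). Dose at week w = min(16, 2 + 2w).

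- Weeks 0 to 7: 2, 4, 6, 8, 10, 12, 14, 16. These match the 5.8 table row by row.
- 8 is reached at (8 − 2)/2 = Week 3; 16 is reached at (16 − 2)/2 = Week 7.
- At Week 12 a child on schedule has been at 16 for 12 − 7 = 5 weeks.
- Shortfall of the Week 12 figure: (16 − 8)/2 = 4 steps; 8/16 = 50%.

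So 16 is the plan's own figure, and no reading of the titration rule makes 8 the maximum.

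**Step 2: who is exposed.** A child at 16 is unaffected. A child at 8 who cannot tolerate more is correctly described by the sentence's second alternative, the maximally tolerated dose. That leaves a child at or near 8 at Week 12 who could still go up. The documents give no figure for how many of the 20 this might be.

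**Step 3: PESQs on the final dose by Week 20.** Let w be the week of the last increase. PESQ visits are 2, 4, 8, 12 and 16. An increase made at a visit is taken to follow that visit's PESQ, so the count is the number of PESQ visits later than w. Weeks on dose at the last PESQ = 16 − w. With an added Week 20 PESQ the count rises by one and the time on dose becomes 20 − w.

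| Last increase (w) | PESQs on final dose | Weeks on dose at last PESQ | Weeks on dose at Week 18 contact | With Week 20 PESQ: count, weeks on dose |
|---|---|---|---|---|
| 7 | 3 (Weeks 8, 12, 16) | 9 | 11 | 4, 13 |
| 8 | 2 (Weeks 12, 16) | 8 | 10 | 3, 12 |
| 9 | 2 | 7 | 9 | 3, 11 |
| 10 | 2 | 6 | 8 | 3, 10 |
| 11 | 2 | 5 | 7 | 3, 9 |
| 12 | 1 (Week 16) | 4 | 6 | 2, 8 |
| 13 | 1 | 3 | 5 | 2, 7 |
| 14 | 1 | 2 | 4 | 2, 6 |
| 15 | 1 | 1 | 3 | 2, 5 |

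Week 7 is the last step in 5.8. Week 8 is shown because section 3.2 says "Week 8 should be the last increase if the participant increases by this schedule" and the Week 8 text of 5.6 also has an increase. The ±3 day window on the Week 16 visit turns 4, 3, 2 and 1 weeks into 25–31, 18–24, 11–17 and 4–10 days.

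**Step 4: is late titration foreseen?** The Week 8 row of 5.8 lets the on-target bloodwork fall anywhere in Weeks 8 to 16, and the Week 16 text provides for a target dose only then reached. A last increase in Weeks 12 to 15 is 12 − 7 = 5 to 15 − 7 = 8 weeks behind the 5.8 schedule: allowed for, but not expected.

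**The case against.** **On the dose figure.** The sentence describes where a child should be by Week 12; it is not a titration order, and it goes straight on to allow the maximally tolerated dose. The correct maximum appears in many other places, including the dosing table that staff would consult. This stands as a limit on the consequence, but it does not make 8 correct. A reader might infer that the protocol caps the dose at 8, or that the tolerated-dose result is generally compromised. The documents support neither: a child following the schedule passes 8 at Week 3.

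**On the PESQ.** A PESQ is taken at the start of the primary window, and section 3.2 holds the dose from then on. The Week 18 contact asks about dosing and tolerability, section 5.7 has adverse events assessed at every such contact, the diary continues, and staff can be reached at all hours. By Week 20 the PESQ is scheduled five times, more often than the QOLCE (three at most), the EEG (twice) or the Vineland (twice). The Week 12 sentence itself expects titration to be over. The Week 16 sentence can also be read as letting the PESQ fall anywhere in Weeks 16 to 20; that would still be one PESQ, though possibly a later one. All of this stands, which is why the point is optional.

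Two stronger readings are tempting. One is that tolerability goes unassessed in Weeks 16 to 20, or that the tolerated dose depends on the PESQ. It does not: section 2 lists blood tests, AED levels, parent report and physician assessment as well, the study team decides, and no PESQ threshold is set. The other is that some children may have no PESQ on their final dose. No passage schedules an increase at or after the Week 16 visit, so that is not shown.

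**Conclusion.** The dose conflict is real and should be corrected. The Week 12 text of 5.6 names 8 mg/kg/day as the maximum where the rest of the plan says 16. The likely harm is confined to slow titrators who could still go up, and to their on-target bloodwork. Their number is unknown. No statistical figure changes: the analysis is descriptive, and the 20 children are a sample of convenience.

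The PESQ point is secondary. None is scheduled between the Week 16 visit and the Week 20 report, but most of that gap is covered by other means. It matters only for children whose last increase falls in Weeks 12 to 15, who have one PESQ on the final dose, at 4 to 1 weeks; there may be none of them. It rests on the natural reading that the PESQ belongs to the Week 16 visit, as section 7.2 and the 5.8 table indicate. A child who stops at Week 20 also has no scheduled PESQ after Week 16. Section 4.4.2 offers one on withdrawal but does not say whether declining the extension counts.

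**What to change.** **Correct the dose (should be done).** In the Week 12 paragraph of 5.6, change 8 to 16 and remove the duplicated alternative, for example: *By Week 12 each child is expected to be at 16 mg/kg/day CBD, or at the highest dose the study team has judged tolerable.* Cost: one figure and a tidied sentence.

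**Add one PESQ (optional).** In 5.6 for Weeks 16–20 and in the matching row of 5.8, add: *When the Week 16–20 seizure diary is collected, the parent or guardian of every child still on TIL-TC150 completes one further PESQ.* Keep the Week 16 PESQ, and apply the addition to all children so that side effects are sought equally often. The plan does not say how the diary is collected, so allow paper, phone or email if there is no visit. Cost: two sentences and at most 20 questionnaires, with no clinic visit added; the downside is one more form per family. For last increases in Weeks 12 to 15 it gives two PESQs on the final dose, the later one at 8 to 5 weeks.
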